8.4 Rationale for Selection of Starting Dose of cePolyTregs

The initial dose, route and regimen of cePolyTregs for Part 1 is proposed as a single dose of 1×10^8 cells by IV infusion over approximately 10 ml/min. This was selected based on a combination of practical considerations of manufacturing capacity, a predicted efficacious dose based on the expected Treg numbers in subjects, and the available safety data of the PolyTregs product currently in clinical trials for various indications.

8.4.1 Dosing Estimate Based on Rodent Models

The effective dose of cePolyTregs for controlling inflammation in ARDS in humans is currently unknown but there are indications from rodent studies. In a mouse model of LPS-induced and viral infection-induced ARDS, a single infusion of 1 million syngeneic Tregs was effective in disease prevention (D'Alessio 2009). Using the traditional exponential allometry for molecular therapy, 1 million cells per dose in a 20 g mouse would translate into ~400 million cells in a 70 kg human with an exponent of 0.75.

There are a number of limitations to this estimate. 1) No dose titration experiments in mice were reported so the minimal effective dose or optimal dose may be different from the estimated 1 million cells. 2) There is no established method for allometric scaling of cellular therapies that have distinct PK and PD from molecular therapies. 3) Mouse models of ARDS used syngeneic (i.e. autologous) Tregs. Allogeneic cePolyTregs proposed for this study contain 10% to 20% of cells that are reactive to mis-matched HLA combined with the existing self-antigen recognition repertoire. These cells are expected to be activated after infusion and proliferate in the recipient, which may potentiate the impact of the infused dose. 4) The Tregs used in studies of mouse models used mouse Tregs whereas the cePolyTregs proposed for use in this study are human Tregs. Due to interspecies incompatibilities of intercellular communications, testing human Treg products limits the utility of mouse models.

Thus, the actual effective dose of cePolyTregs in humans cannot be accurately estimated based on available animal data. The ~400 million cells per dose estimate can be viewed as a reference at best and thus is proposed as the top dose being explored in the current study.

8.4.2 Manufacturing Capacity

Since the inception of UCSF's Treg cell therapy programs, we have produced 43 PolyTregs doses in our GMP facility. For all these products, 1 unit of blood, or $\sim 500 \times 10^6$ PBMCs were used as starting materials for Treg cell manufacture. [Table 1](#) summarizes the manufacturing experience which is used to estimate manufacturing capacity.

Table 1. Manufacturing Capacity of Analogous, Autologous Product PolyTregs

Quartile	Treg Yield (number of cells)		
	Day 0	Day 12	Day 14
Median	4.2 million	578 million	1.5 billion
75 th percentile	6.0 million	1.0 billion	3.0 billion
25 th percentile	2.7 million	299 million	716 million

The manufacturing process for cePolyTregs will be the same as that for PolyTregs with the following 3 major distinctions: 1) cePolyTregs will be sourced from qualified healthy donors; 2) leukapheresis will be used so more Tregs can be collected on Day 0; and 3) products will be harvested on Day 12 instead of Day 14 of manufacture. We expect Day 0 cell yield to be on the higher end of our previous experience since donors can be prescreened for higher numbers of Tregs in blood. Additionally, each leukapheresis will yield 10 billion PBMCs, 20x that in one unit of blood. Thus, we can expect Day 0 cePolyTregs yield to be 20x higher than that in [Table 1](#). Using a conservative estimate of 20 million Tregs on Day 0 and assuming a similar expansion rate as previously observed, we can expect a yield of ~3 billion cells at the Day 12 cePolyTregs harvest. This would translate into 30 doses at 100 million, 15 doses at 200 million, and 7 doses at 400 million cells. More donors can be recruited to repeat the process to scale production.

8.4.3 Safety of T Cell Therapy

Collective experiences with Treg cell therapy during the past 11 years has shown the therapy is generally safe and well tolerated ([Esensten 2018](#)).

The highest dose of autologous PolyTregs tested for safety in the Phase 1 Treg study in diabetes was 2.6×10^9 (range 2.35 to 2.94×10^9). Adverse events in the trial have generally been mild or moderate in severity. The most common adverse events have been related to mild upper respiratory infections. In the 24 hours following infusion, only 4 adverse events in 4 subjects were reported. Two were mild headache, one was mild nausea, and one was mild abdominal pain. Thus, infusion reactions have been limited.

Laboratory abnormalities have reflected protocol-specified phlebotomy. There have been minor elevations in lactate dehydrogenase (LDH) likely due to concomitant infection or minor trauma. One subject had notable transient elevations in transaminases and LDH subsequently determined to be due to intercurrent cytomegalovirus infection.

Finally, in the study described in Section [7.4](#) in which 2 subjects with COVID-19-related ARDS received infusions of cord-blood-derived Tregs (2 doses of 1×10^8 cells/dose in 1 subject and 3 of the same doses in the other) the doses were well-tolerated and clinical improvement was evident within 48 hours of infusion ([Gladstone 2020](#)). Although those cells were sourced differently, those results provided a reference point for selecting the starting dose for this trial.

UCSF	Clinical Study Protocol No. UCSF-cePolyTregs-01	Page 33 of 72
------	---	---------------

8.5 Study Objectives

8.5.1 Primary Objectives

Parts 1 and 2: To evaluate the safety and tolerability of cePolyTregs administered as a single IV dose in subjects with ARDS associated with SARS-CoV-2 infection

Part 2 (Phase 2a): To evaluate the efficacy of cePolyTregs administered as a single IV dose in subjects with ARDS associated with SARS-CoV-2 infection

8.5.2 Secondary Objectives

Part 1 (Phase 1): To determine the RP2D of cePolyTregs administered as a single IV dose in subjects with ARDS associated with SARS-CoV-2 infection

Parts 1 and 2: To determine the pharmacodynamics and biomarker changes associated with cePolyTregs administration as a single IV dose in subjects with ARDS associated with SARS-CoV-2 infection

8.5.3 Exploratory Objective

To determine the clinical activity of a single IV dose of cePolyTregs on extrapulmonary manifestations of infection with SARS-CoV-2

8.6 Endpoints

8.6.1 Primary Endpoints

Part 1 (Phase 1):

Safety and tolerability of cePolyTregs as assessed by DLTs, defined as any related treatment-emergent adverse event (TEAE) with an NCI CTCAE 5.0 grade ≥ 3 which also represents a shift from baseline clinical status of ≥ 1 NCI CTCAE grade.

Part 2 (Phase 2a):

Efficacy of cePolyTregs compared with placebo/SOC, as assessed by time to recovery, defined as the first day during the 28 days after randomization on which a subject meets the criteria for category 0, 1, 2, 3, or 4 on the WHO severity scale for COVID-19 pulmonary syndrome.

Safety of cePolyTregs as assessed by the occurrence of related TEAEs with an NCI CTCAE 5.0 grade ≥ 3 .

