5.2 Schedule of Events

Procedure	Study Period	Screening Period	Treatment Period								Safety Follow-up Period		
			Up to 72 hours	0 (Pre-dose)	0.5 (Post-dose) ^b	4 ± 1	7 ± 1	14 ±2	21 ±2	28 ±2	42 ±2	56 ±2	84 ±2 or ET
Consent		X											
Eligibility criteria review		X	X										
Demographics ^c		X											
Medical/surgical histories		X											
Vital signs ^d		X	X	X	X	X	X	X	X	X	X		X
Physical examination ^e		X	X	X	X	X	X	X	X	X	X		X
Concomitant medications		X	X	X	X	X	X	X	X	X	X		X
AE Assessment		X	X	X	X	X	X	X	X	X	X		X
12-lead ECG		X		X					X				X
Efficacy assessments ^f		X		X	X	X	X	X	X	X	X		X
Chest imaging ^g		X	X	X			X	X	X	X	X		X
Ventilation Parameters ^h			X	X	X	X	X	X	X				
Randomization (IWRS, Part 2 only)				X									
Investigational Product administration				X									
Local Labs													
Hematology		X	X	X	X	X	X	X	X	X	X		X
Serology ⁱ		X											
Serum chemistry		X	X	X	X	X	X	X	X	X	X		X
High sensitivity troponin		X	X	X	X	X	X	X	X	X	X		X
d-dimer		X	X	X	X	X	X	X	X	X	X		X
Acute phase reactants (ferritin, CRP)		X	X	X	X	X	X	X	X	X	X		X

UCSF	Clinical Study Protocol No. UCSF-cePolyTregs-01	Page 18 of 72
------	---	---------------

Study Period	Screening Period	Treatment Period								Safety Follow-up Period		
		Study Day ^a										
Procedure	Up to 72 hours	0 (Pre-dose)	0.5 (Post-dose) ^b	4 ± 1	7 ± 1	14 ± 2	21 ± 2	28 ± 2	42 ± 2	56 ± 2	84 ± 2 or ET	
Urinalysis	X	X	X	X	X	X	X	X	X	X	X	
Pregnancy test (urine) ^j	X								X	X	X	
Mechanistic Collections												
Endotracheal Aspirate ^k		X	X	X	X	X	X	X				
Mini BAL ^{k,l}		X	X	X	X	X	X	X				
Whole blood		X	X	X	X	X	X	X		X	X	
Urine		X	X	X	X	X	X	X				

Abbreviations: AEs = adverse events; CRP = C-reactive protein; D = Day(s); ECG = electrocardiogram; ET = early termination; HBsAg = hepatitis B virus surface antigen; HCV = hepatitis C virus; HIV = human immunodeficiency virus; IP = investigational product; IWRS = Interactive Web Response System; min = minute(s); PD = pharmacodynamic.

^a Safety (e.g., AE assessments, vital signs, physical examinations) and efficacy assessments will be performed daily during the period in which subjects remain hospitalized.

^b Assessments should be measured at 12 hours (± 6 hours) post dose.

^c Includes subject's sex, age, race, and ethnicity.

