8.8.6 Study Discontinuation

The study may be stopped at the discretion of the Sponsor based on recommendations of the DSMB. The study may also be stopped pending DSMB evaluation of all available safety and PD data if any of the following occur:

- Any study drug-related death
- The occurrence of 3 deaths within 28 days post treatment in the first 5 subjects treated or, subsequent to the first 5 subjects, the observed mortality rate across the cumulative population of treated subjects exceeds the anticipated mortality rate of 50%
- Two CTCAE Grade 4 or 5 TEAEs that are deemed related to study drug
- An increase in the incidence of infections of special interest (pneumonia or infections involving pathogens not anticipated in a COVID-19 setting) beyond the expected background incidence

If the DSMB recommendation is to interrupt study dosing for all subjects or to pause enrollment, study dosing can be resumed, based on the recommendation of the DSMB, only after further review of all available safety data and applicable notifications of submission to appropriate regulatory agencies and institutional review committees, in line with country-specific regulations.

All deaths occurring during the study will be reviewed promptly by the DSMB as they occur. If at any point following enrollment of the first 5 subjects, the observed mortality rate across the cumulative population of treated subjects exceeds the anticipated mortality rate of 50%, the study will be halted.

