9.1 Inclusion Criteria

1. Diagnosis of ARDS and respiratory failure requiring mechanical ventilation for less than 72 hours at the time of enrollment
2. $\text{PaO}_2/\text{FiO}_2 < 300$ and PEEP > 5
3. Male or female, age 18 to 70 years at Screening
4. Weight > 40 kg
5. Documented diagnosis of infection with SARS-CoV-2 virus by PCR
6. Chest imaging (radiograph or CT scan) with abnormalities consistent with COVID-19 pneumonia that could not be explained by effusions, pulmonary collapse, or nodules; and respiratory failure that could not be explained by cardiac failure or fluid overload
7. Females of childbearing potential and males must use effective contraception practices from Screening until 28 days after the EOS visit
8. Females of childbearing potential must have a negative pregnancy test at Screening and within 24 hours prior to dosing of study drug
9. Able to provide Informed Consent, either by self or by medical proxy
10. Willing and able to comply with this protocol for the entire duration of the study

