11.6 WHO Severity Scale for COVID-19 Pulmonary Syndrome

The WHO ordinal severity scale ([Figure 2](#)) was derived by a special WHO committee to measure illness severity over time ([World Health Organization 2020](#)). Subject status will be assessed using the severity scale at the intervals described in the SOE.

Figure 2. WHO Ordinal Scale for COVID-19 Clinical Improvement

Patient State	Descriptor	Score
Uninfected	No clinical or virological evidence of infection	0
Ambulatory	No limitation of activities	1
	Limitation of activities	2
Hospitalized Mild disease	Hospitalized, no oxygen therapy	3
	Oxygen by mask or nasal prongs	4
Hospitalized Severe Disease	Non-invasive ventilation or high-flow oxygen	5
	Intubation and mechanical ventilation	6
	Ventilation + additional organ support – pressors, RRT, ECMO	7
Dead	Death	8

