13.1 General Considerations

Part 1 (Phase 1)

Analyses for the primary safety endpoint will be descriptive. AEs will be classified using MedDRA version 20.0 or higher. The severity of the toxicities will be graded according to the NCI CTCAE version 5.0.

Part 2 (Phase 2a)

In the randomized, Phase 2 portion of the study, the primary efficacy endpoint is time to recovery, defined as the first day during the 28 days after randomization on which a subject meets the criteria for category 0, 1, 2, 3, or 4 on the WHO severity scale for COVID-19 pulmonary syndrome. The intent-to-treat (ITT) analysis will be carried out for the primary efficacy endpoint. Subjects will be analyzed according to the assigned treatment group, regardless of whether the subjects receive any study treatment or receive a different study treatment from that to which they were randomized. The primary analysis will be a stratified log-rank test of time to recovery with cePolyTregs compared with placebo/SOC, with stratification by WHO severity scale for COVID-19 pulmonary syndrome at enrollment. The test will be performed with a two-sided type I error rate of 10%. Data for subjects who fail to recover or die will be censored at Day 29.

Analysis of the primary safety endpoint will be descriptive according to the intervention received and no formal comparisons between the 2 study arms will be performed. The safety analysis set will consist of all subjects who received at least 1 dose of study drug. AEs will be summarized by dose cohort using numbers and proportions.

The assessment of PD and biomarker data are described in [Appendix C Mechanistic Assessments](#).

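### One day at WHO category 0–4 counts as recovery, so a subject extubated for comfort care who then dies can be scored a success, and the Day 29 censoring sentence leaves the coding of such deaths open

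*Combined protocol and SAP*

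**What the plan says.** Section 8.6.1 defines the Part 2 primary efficacy endpoint, time to recovery, on the WHO scale in these words: "the first day during the 28 days after randomization on which a subject meets the criteria for category 0, 1, 2, 3, or 4". The synopsis (Section 5.1, Endpoints and Statistical Methods) and Section 13.1 repeat this. None of them requires that the state last or that the subject survive, and none mentions re-intubation or withdrawal of ventilation for comfort care.

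- **Scale (Section 11.6).** Category 4 is "Oxygen by mask or nasal prongs". Category 3 is in hospital without oxygen. Category 5, which is not recovery, is "Non-invasive ventilation or high-flow oxygen".
- **Entry (Section 9.1).** Subjects have "respiratory failure requiring mechanical ventilation for less than 72 hours at the time of enrollment", so all start at category 6 or 7.
- **Scoring (Section 5.2, footnote a).** The footnote says that "efficacy assessments will be performed daily during the period in which subjects remain hospitalized". No rule says which score represents a day.
- **Mortality (Section 8.8.6).** The study halts if cumulative mortality "exceeds the anticipated mortality rate of 50"%. No time horizon is attached.
- **Censoring (Section 13.1 and synopsis).** "Data for subjects who fail to recover or die will be censored at Day 29".

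The synopsis and Section 13 leave analysis detail to a separate statistical analysis plan. Nothing in the available text settles how comfort-care extubation or death after recovery is coded.

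**The concern.** Because everyone starts ventilated, the primary event is in practice leaving the ventilator for mask, prongs or no oxygen. Categories 3 and 4 record the device and not why it changed. A subject whose ventilation is withdrawn because the goals of care have changed can be scored 3 or 4 at the next daily assessment and die soon after. With mortality of 50% anticipated, such deaths cannot be assumed rare.

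The error has a direction. If cePolyTregs lowers mortality, the false recoveries fall mainly in the placebo arm and hide benefit. If it raises mortality, they fall mainly in the active arm and resemble efficacy. Appendix B leaves the final step of removing support to the clinical team, and Sections 10.2 and 10.7 leave site staff other than investigators unblinded. A one-day event is more exposed to such decisions than a lasting one.

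Separately, two analysts could code a death after recovery differently, each with a sentence of the protocol in support.

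**Working it through.** **1. The two rules side by side.** The courses are hypothetical.

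| Course | Section 8.6.1 | Day 29 sentence, literal | Day 29 sentence, read as deaths without recovery |
|---|---|---|---|
| Never at 0–4, alive or dead | no event | censored | censored |
| Mask Day 8, re-intubated Day 9, alive at Day 29 | event Day 8 | not covered | not covered |
| Mask Day 8, re-intubated Day 9, dies Day 20 | event Day 8 | censored | event Day 8 |
| Comfort-care extubation to mask Day 10, scored 4, dies Day 12 | event Day 10 | censored | event Day 10 |

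The rules can diverge only in the last two rows.

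**2. The plan's own power (Section 13.2).** Inputs: 67/252 recovered by Day 14 on control, median 16 days on active, 50 per arm, two-sided 10%.
- Control rate = −ln(1 − 67/252)/14 = 0.02208 per day. The median is ln 2/0.02208 = 31.4 days, and 28-day recovery is 1 − exp(−28 × 0.02208) = 46.1%.
- Active: 1 − 2^(−14/16) = 45.5% and 1 − 2^(−28/16) = 70.3% (stated as 70.2%). The rate ratio is 1.962.
- Expected events = 50 × 0.461 + 50 × 0.703 = 58.2.
- Freedman: √58.19 × (0.962/2.962) − 1.645 = 0.833, so power is 79.8%. Schoenfeld gives 82.3%. Simulation in whole days gives 82.1% unstratified, and 81.4% stratified with an assumed even split of categories 6 and 7.

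The stated 80% reproduces.

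**3. If the planned benefit is real.** Let q be the share of Day 28 deaths scored 4 or better once. The documents do not give q; the assumed range is 5–30%. Further assumptions: mortality 50% control and 27% active; Section 13.2 rates free of such cases; false-recovery days uniform over Days 2–28 in the first simulation. The scenario is feasible without overlap between recovery and death: 46.1 + 50 = 96.1% and 70.2 + 27 = 97.2%.

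Counted recoveries are 50 × (0.461 + 0.50q) on control and 50 × (0.702 + 0.27q) on active. The two power columns are independent simulations of 4,000 and 3,000 trials.

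| q | Control | Active | Difference | Power, first | Power, second |
|---|---|---|---|---|---|
| 0 | 23.1 | 35.1 | 12.1 | 83% | 81% |
| 5% | 24.3 | 35.8 | 11.5 | 79% | 80% |
| 10% | 25.6 | 36.5 | 10.9 | 77% | 77% |
| 20% | 28.1 | 37.8 | 9.8 | 71% | 72% |
| 30% | 30.6 | 39.2 | 8.6 | 65% | 65% |

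**4. If active treatment raises mortality.** Assume true recovery of 40% in both arms and mortality of 35% control versus 55% active. Counts are 50 × (0.40 + 0.35q) and 50 × (0.40 + 0.55q).

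| q | Control | Active | Significant in favour of active (nominal 5%), two simulations |
|---|---|---|---|
| 10% | 21.8 | 22.8 | 6–7% |
| 20% | 23.5 | 25.5 | 11% |
| 30% | 25.3 | 28.3 | 14–15% |

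When the false share is the same in both arms (10% of non-recoverers) and treatment has no effect, two-sided rejection is 10.3%. The inflation therefore needs a difference between arms.

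**5. Cost of stricter coding.** Suppose instead that a share f of the recoveries planned in Section 13.2 would be recoded as non-recovery, equally in both arms. Simulated power goes from 82% to 77% (f = 5%), 73% (10%), 64% (20%) and 56% (30%). At f = 10%, 60 per arm restores 80%. At f = 20%, 70 per arm gives 77%.

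**The case against.** - **The Day 29 sentence may be harmless.** It can naturally be read as covering only deaths without a prior recovery, since a first-event time is not usually undone by later data. This stands as a reading and makes the problem an ambiguity. But that reading confirms the dying comfort-care subject as a recovery, so one of the two problems remains either way.
- **The scale is not purely respiratory.** It also scores pressors, renal replacement, activity and infection, and it lists categories 3 and 4 under mild disease. Whether a dying subject meets them is therefore arguable. Extubation to high-flow oxygen or non-invasive ventilation is category 5 and does not count. This narrows who is affected; the descriptors themselves still turn on the device.
- **The power loss may be partly counted twice.** Section 13.2 takes its control rate from subjects achieving a score of 4 or better, with no durability condition, so transient cases may already be in the 46.1%. This stands. The loss in step 3 of the working holds only if they are not; if they are, stricter coding costs power as in step 5.
- **There are safeguards.** Weaning is protocolised (Section 11.13, Appendix B), investigators are blinded, and ventilation status, ventilator-free days and mortality are secondary endpoints (Section 8.6.3). A mortality difference would be visible, but none of this changes the primary event.

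A reader might infer three stronger things that the documents do not support. First, that a re-intubated subject gets two outcomes: one alive at Day 29 simply keeps the event. Second, that the trial cannot answer its efficacy question: that depends on a rate nobody has stated. Third, that a sustained-recovery primary endpoint is required: that is a debatable design choice, and a 48-hour window has no basis in the text.

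**Conclusion.** The point holds in a limited form. As written, the primary endpoint can count a subject who dies after comfort-care extubation as recovered, and the coding of anyone who reaches category 0–4 and dies by Day 28 is open to two readings. This rests on the wording alone.

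The size rests on assumptions. With q of 5–30%, power falls from about 82% to about 79–65%, given 50% versus 27% mortality and planning rates free of such cases. With 20 points more mortality on active treatment, the bias towards active is small at q = 10% (about 1 subject) and material at 20–30% (about 2 to 3 subjects, with false positives in its favour at roughly two to three times the nominal 5%). No arithmetic error in Section 13.2 is alleged. The case for change rests on what the endpoint counts and on the direction of the error more than on any one of these figures.

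**What to change.** Before any Part 2 outcome data are seen, amend the synopsis (Endpoints and Statistical Methods), Section 8.6.1 and Section 13.1 to state that:

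- (a) category 3 or 4 reached by withdrawing ventilation for comfort care is not recovery;
- (b) subjects who die by Day 28 are non-recoveries censored at Day 29, even if they had an earlier day at category 0–4, and all other subjects, including those re-intubated and alive, keep their first-day event.

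State also which score represents a day. Prespecify two sensitivity analyses: the single-day definition as it stands, and sustained recovery (for example 48 hours alive at category 0–4). The second needs a rule for first days on Day 27 or 28 and for discharged subjects, who are no longer scored daily.

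The cost is wording plus one eCRF field for comfort-care extubation; daily in-hospital scores and deaths are already collected. Slightly fewer recoveries will be counted, and a subject who truly recovers but dies of another cause by Day 28 becomes a non-recovery. The Section 13.2 power should therefore be re-run under the revised coding with a stated share of recoded recoveries. These changes concern outcome coding only and leave patient care unchanged.
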